11.7 Analysis of safety data

Adverse events will be listed and/or summarized. Device deficiencies and concomitant medications will be listed.

11.8 Sample size

Input for the sample size calculations i.e., frequencies, rates, means and standard deviations are based on three exploratory studies CP322, CP323 and CP324. The studies investigated earlier prototypes of the micro-hole zone catheter with identical or similar endpoints in populations of both IC users and healthy volunteers.

A sample size for the primary endpoint of residual urine at 1st flow stop (RV1) is judged to be accommodated by 30 subjects with a power above 90%, assuming a difference of 40 mL, a $sd_{comparator}$ of 50 mL and a sd_{active} of 10 mL. (please see table 11-1). Taken into consideration a discontinuation of 20%, the endpoint of RV1 is sufficiently supported by randomising at least 36 subjects.

For primary endpoint of flow stop episodes a sufficient sample size is judged to be accommodated by 35 subjects with a power above 90%, assuming a difference of 1 flow stop with a $\lambda_{comparator}$ of 2 flow stop, and a λ_{active} of 1 flow stop (please see table 11-2). Taken into consideration a discontinuation of 20%, the endpoint of RV1 is sufficiently supported by randomising at least 42 subjects.

Aiming for an acceptably narrow 95% confidence interval, for the difference in frequency of positive haematuria events, sufficient inference is judged to be accommodated with 60 subjects completing the study (please see table 11-3). Taken into consideration a discontinuation of 20%, the aim is to randomise at least 72 subjects.

72 subjects should at least be randomised in support of the secondary endpoint of positive haematuria frequency and a sub-set of subjects, at least 42, should be randomised in support of the primary endpoints RV1 and number of flow stop episodes.

Table 11-1 Sample size calculation of Residual urine at 1st flow stop in a cross-over design, solving for varying power and number of subjects, assuming no within subject correlation as a worst-case approach, using proc Power in SAS.

μ (sd) comparator	μ (sd) active	Alpha	Power	Sample size
50 (90)	10 (15)	0.05	86.0 %	25
50 (90)	10 (15)	0.05	90.0 %	28
50 (90)	10 (15)	0.05	91.6 %	30

Table 11-2 Sample size simulation of Flow stop events in a cross-over design, solving for varying power and number of subjects, assuming no within subject correlation as a worst-case approach, using a generalised linear mixed model with proc Glimmix in SAS.

λ comparator	λ active	Alpha	Power	Sample size
2	1	0.05	81.2 %	25
2	1	0.05	88.0 %	30
2	1	0.05	92.2 %	35

Table 11-3 Sample size simulation of the positive haematuria frequency in a cross-over design, assuming 10 repeated measurements in each period and a within subject correlation of 50%, solving for varying frequencies and power, with a fixed sample size of 60 subjects, using a generalised linear mixed model with proc Glimmix in SAS.

P comparator	P active	Alpha	Power	Sample size
20 %	14 %	0.05	65.0 %	60
20 %	13 %	0.05	90.0 %	60
20 %	12 %	0.05	98.0 %	60

If the discontinuation exceeds 20% i.e., the number of subjects completing the study, is likely to be less than 60 subjects, additional subjects will be included (subjects replaced), to ensure at least 60 subjects completing and thereby maintain sufficient power in the study.

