11.9 Level of significance and power

A significance level of alpha 0.05 (2-sided) will be applied.

The power for concluding superiority of the investigational device is at least 90% or higher.

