11.10 Pass/fail criteria

To demonstrate superiority of the investigational device, the null hypothesis of the primary endpoints must be rejected, at a 5% significance (alpha 0.05).

The pass criteria for the study are based on the results from analysing the two primary endpoints in a hierarchical fashion: rejecting the null-hypothesis on the first endpoint (Residual urine at first flow-stop) before continuing to the second (Number of flow-stop episodes).

12 Data management

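### Table 11-1 does not give the stated RV1 power at its listed sample sizes (64.1% at 30 subjects on its own inputs, against 91.6% stated), and the text of 11.8 gives different SDs

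*Combined protocol and SAP*

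**What the plan says.** Section 11.8 says the planning inputs, including "means and standard deviations are based on three exploratory studies CP322, CP323 and CP324". For RV1 it states that the sample size "is judged to be accommodated by 30 subjects with a power above 90%, assuming a difference of 40 mL", with a comparator SD "of 50 mL and a sd_{active} of 10 mL" for the active device, and it points to Table 11-1.

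Table 11-1 lists mean (SD) 50 (90) for the comparator and 10 (15) for the active device in all three rows. Its stated powers are 86.0%, 90.0% and 91.6% at sample sizes 25, 28 and 30. Its caption describes a crossover, "assuming no within subject correlation as a worst-case approach, using proc Power in SAS".

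The text treats 30 as the total number of subjects and inflates it to 36 for 20% discontinuation. The flow-stop endpoint needs 35 completers, inflated to 42, and this sets the subgroup: "a sub-set of subjects, at least 42, should be randomised in support of the primary endpoints RV1 and number of flow stop episodes".

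Section 11.9 states: "A significance level of alpha 0.05 (2-sided) will be applied" and "The power for concluding superiority of the investigational device is at least 90% or higher". Section 11.10 makes the pass decision hierarchical: "rejecting the null-hypothesis on the first endpoint (Residual urine at first flow-stop) before continuing to the second (Number of flow-stop episodes".

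**The concern.** There are two separate problems. First, the SDs in the text (50 and 10) are not those in the table that the text cites (90 and 15); they equal the table's means. Second, the powers in the table look too high for a 40 mL difference with an SD of 90 in one arm and no correlation to offset it.

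RV1 is the first test in a fixed sequence and a condition for passing the study, so its power is a ceiling on the chance of passing. Table 11-1 is the only numerical support for that power. If its sample sizes are wrong, the subgroup of 42 was set by the flow-stop calculation alone, and no valid calculation shows that it is large enough for RV1. The rule in 11.8 for replacing subjects protects 60 completers overall, not completers in this subgroup.

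**Working it through.** **Inputs.** Difference 40 mL (50 − 10), SDs 90 and 15, correlation 0 (Table 11-1 and its caption); two-sided alpha 0.05 (11.9); one value per device per subject, analysed in a mixed model with random subject and fixed visit and device (11.4). With complete data this is in effect a paired comparison.

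**Formula.** SD of the within-subject difference = √(90² + 15² − 2ρ·90·15). At ρ = 0 this is √8325 = 91.24 mL. Power is from the noncentral t distribution with n − 1 degrees of freedom and noncentrality 40 / (91.24/√n).

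**The plan's own rows.** At n = 30 the standard error is 91.24/√30 = 16.66, the noncentrality is 40/16.66 = 2.40 and the critical value is 2.045, which gives 64.1%.

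| Listed n | Stated power | Power at listed n | Power at twice the listed n |
|---|---|---|---|
| 25 | 86.0% | 55.7% | 86.0% (50 pairs) |
| 28 | 90.0% | 60.9% | 89.7% (56 pairs) |
| 30 | 91.6% | 64.1% | 91.6% (60 pairs) |

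**Other readings at n = 30.**
- One-sided test: 75.8%.
- Normal approximation: 67.0%.
- Two-sample t-test with 30 per group: 64.3% to 65.6%.
- Correlation 0.5 (SD of difference 83.5): 71.8%.
- Correlation 1 (SD of difference 75): 80.6%. So under normal theory no correlation reaches 90% at 30.
- Root-mean-square SD of 64.5 used as the SD of the difference: 84.5%, 88.5% and 90.7% for the three rows. This is closer, but it does not follow from zero correlation and matches less well than doubling n.
- Text SDs, 50 and 10 (SD of difference √2600 = 50.99): 98.6%. So the text's SDs did not produce the table either.

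Doubling fits best, which suggests that a per-sequence number was carried forward as a total. No code is shown, so this is inference.

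**Power at the planned subgroup (table SDs, normal theory).** 42 less 20% is 33.6.

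| Completers | ρ = 0 | ρ = 0.5 | ρ = 1 |
|---|---|---|---|
| 33 | 68.5% | – | – |
| 34 | 69.9% | – | – |
| 35 | 71.2% | 78.6% | 86.5% |
| 42 | 79.2% | 85.8% | 92.1% |

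**Size needed for 90% at ρ = 0.** 57 completers with SDs 90/15 (90.2%); 20 with SDs 50/10 (91.4%).

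**Both primaries at 35 completers.** At most 71.2%, the RV1 power. If the two tests were independent, 0.712 × 0.922 is about 66%, taking the plan's own 92.2% for flow stops.

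**Effect of skewness.** The plan states no distribution for RV1. As an assumption to show the range, independent values with the table's means and SDs were simulated and analysed with a paired t-test (40,000 runs):

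| Assumed shape | n = 30 | n = 35 | n = 42 |
|---|---|---|---|
| Gamma | 81% | 89% | 95% |
| Lognormal | 92% | 95% | 97% |

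**The case against.** The strongest reply is that this shows an inconsistency, not an underpowered trial.

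- With the text's SDs, RV1 has 98.6% power at 30 and 99.5% at 35. Which pair is right depends on pilot data that the plan does not show. This stands, and is why the conclusion below is conditional.
- RV1 is essentially non-negative, so a mean of 50 with an SD of 90 implies a skewed distribution, and normal-theory power may be too low. At 35 completers the range runs from 71% (normal) to 95% (lognormal). This also stands. It does not rescue Table 11-1, which names a standard procedure and states no skewed distribution, while 11.4 analyses RV1 in a general linear mixed model.
- The table is reproducible if its sample size means subjects per sequence. But the caption speaks of the number of subjects, and the text inflates 30 to 36 as a total. If 30 were per sequence, 60 completers would be needed, and a subgroup of 42 cannot supply them.
- 42 is a minimum, so more subjects may be measured. That is so, but the flow-chart footnote in 8.11 treats it as the number, and even 42 completers give 79.2% on the table's inputs.
- The 66% figure assumes independence, yet section 6.3 attributes both endpoints to mucosal suction, so positive dependence is more likely. Agreed: 66% is illustrative. The ceiling set by RV1 does not need independence.

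**Conclusion.** The concern holds. At the listed sample sizes, Table 11-1 overstates the power that follows from its own inputs by about 27 to 30 percentage points (91.6 − 64.1 = 27.5 at 30 subjects; 86.0 − 55.7 = 30.3 at 25). The SDs in the text contradict the table, and neither pair yields the stated powers at those sizes.

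If the table's SDs are right, then with zero correlation and normal theory RV1 power is 68.5% to 71.2% at 33 to 35 completers and 79.2% at 42, and the claim in 11.9 is not met. If the text's SDs are right, RV1 is amply powered and the table is wrong. A skewed RV1 distribution could bring power near or above 90% at the planned size, but the plan does not invoke one. Section 11.9 also does not say whether its figure covers one primary endpoint or both. Type I error and the analysis model are unaffected. What fails is the power justification for the endpoint on which passing depends, and that must be corrected.

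**What to change.** 1. Check the SDs against CP322, CP323 and CP324 and use one pair in both the text of 11.8 and Table 11-1.
2. State whether the table's sample size is total subjects or subjects per sequence.
3. If 90 and 15 are the SDs, either restate the powers as 55.7%, 60.9% and 64.1% at 25, 28 and 30 subjects, or list 50, 57 and 60 pairs for about 86%, 90% and 91.6%. If 50 and 10 are the SDs, correct the table's inputs and powers.
4. In 11.9, say what the power refers to, preferably the probability of rejecting both primary hypotheses at the planned subgroup size after discontinuation. If the sponsor relies on skewness, it should name the distribution and give the calculation under it.

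The cost is a text and table change in 11.8 and 11.9 and one recomputation from pilot data the sponsor already holds. The stated power may become less favourable. No subjects or procedures are added by this request.

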6.1 General

The investigation is a multi-centre, randomised, controlled crossover study including 72 male IC users. The study will be conducted in Denmark, France, Germany and United Kingdom.

All subjects will have endpoints related to hematuria, catheter perception and quality of life measured during two periods of home-use (test period T1 and T2), while a subgroup of at least 42 subjects will have endpoints related to bladder emptying (residual volume and number of flow-stop episodes), measured at test visits (V2 and V3) at the hospital. Please refer to section 11.8 for further information on sample size.

The total study duration for the individual subject will be approximately nine weeks, consisting of four study visits and two 4-week test periods at home. Visits 0 and 1 can be performed on the same day. For visit 2 and 3, catheterisations will be performed in a hospital setting for bladder emptying assessment (for the above-mentioned subgroup) and urine samples collected (the latter only in Denmark). Visit 1 and 2 are followed by a home-use test period (T1 and T2, respectively), followed by visit 3 which terminates the study.

If the pandemic continues, home visits may be implemented if accepted by the subjects.

[figure not shown]

Figure 6-1 Crossover investigation with two devices.

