7.2 Recruitment, enrolment and inclusion

7.2.1 Definition of recruitment, enrolment, inclusion and completer

Recruitment: Active efforts by investigators to identify subjects who may be suitable for enrolment into a clinical trial. Subjects are selected based on the protocol's inclusion and exclusion criteria during the clinical trial recruitment period.

Enrolment: The process of registering or entering a subject into a clinical trial. Signing of the Informed Consent Form. Once a subject has been enrolled, the participant would then adhere to the clinical trial protocol.

Inclusion: When an enrolled subject fulfils in- and exclusion criteria and can be randomised. A subject included in the study, that – for some reason – decides to withdraw his participation, can be replaced.

Completer: A subject has completed the study if the subject has been enrolled and randomised and have completed treatment period 1 and 2 per protocol and have attended to the visits according to the protocol.

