7.4 Subject replacement

Randomised subjects that for some reason withdraw from the clinical investigation can be replaced. Replacements should be discussed with Sponsor. Please also refer to section 11.8 Sample size for further information.

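### The 72 and 42 to be randomised allow for 16.7% discontinuation, not the stated 20%, and mandatory replacement has no completer count for the subset that carries both primary endpoints

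*Combined protocol and SAP*

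**What the plan says.** Section 11.8 (Sample size) sets three needs: 30 subjects for residual volume at first flow-stop (RV1), 35 for flow-stop episodes and 60 completers for positive haematuria. It applies a 20% discontinuation to each and arrives at 36, 42 and 72. For haematuria it says: "Taken into consideration a discontinuation of 20%, the aim is to randomise at least 72 subjects". The flow-stop paragraph ends: "the endpoint of RV1 is sufficiently supported by randomising at least 42 subjects". It names RV1, but the figure follows from the 35 for flow stops.

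The replacement rule is at the end of the same section. Its trigger is "If the discontinuation exceeds 20% i.e., the number of subjects completing the study, is likely to be less than 60 subjects", and its action is "additional subjects will be included (subjects replaced), to ensure at least 60 subjects completing".

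Section 6.1 says that "a subgroup of at least 42 subjects will have endpoints related to bladder emptying", measured at visits 2 and 3. Section 11.10 bases pass or fail on the two primary endpoints alone, and both come from that subset.

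Elsewhere replacement is only permitted. Section 7.2.1 says that an included subject who "decides to withdraw his participation, can be replaced". Section 7.4 says: "Randomised subjects that for some reason withdraw from the clinical investigation can be replaced", after discussion with the sponsor, and refers back to section 11.8. Section 11.9 states: "The power for concluding superiority of the investigational device is at least 90% or higher".

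**The concern.** There are two linked problems.

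First, each inflated number is the need plus 20% of the need. That is not an allowance for losing 20% of those randomised. The replacement trigger repeats the slip by treating more than 20% discontinuation and fewer than 60 completers as the same event, which they are not when 72 are randomised.

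Second, the one rule that obliges the sponsor to add subjects looks only at the overall count of 60, which was set for a secondary endpoint. The subset that decides the study has a number to randomise (at least 42) but no number of completers to protect. A run of dropouts concentrated in the subset could take flow stops below the plan's own 35 without obliging anyone to act.

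At stake are the accuracy of a stated design figure and whether the safeguard covers the endpoints that matter most.

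**Working it through.** **Inputs.** Needs 30, 35 and 60; stated discontinuation 20%; numbers to randomise 36, 42 and 72 (all section 11.8). Flow-stop power 88.0% at 30 subjects and 92.2% at 35 (Table 11-2). Power claim of at least 90% (section 11.9).

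**1. Reproducing the plan's figures.** Need × 1.2 gives 30 × 1.2 = 36, 35 × 1.2 = 42 and 60 × 1.2 = 72. All three match exactly.

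**2. What a 20% allowance requires.** Need / (1 − 0.20) gives 30 / 0.8 = 37.5 (38), 35 / 0.8 = 43.75 (44) and 60 / 0.8 = 75.

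**3. The allowance actually provided.** 1 − need / randomised:
- Overall: 1 − 60/72 = 16.7%, or 12 losses.
- Subset, flow stops: 1 − 35/42 = 16.7%, or 7 losses.
- Subset, RV1 at its stated need of 30: 1 − 30/42 = 28.6%. Flow stops are therefore the binding endpoint.

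At a true 20% loss, 72 × 0.8 = 57.6 and 42 × 0.8 = 33.6 remain, against 60 and 35.

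**4. The trigger wording.** With exactly 72 randomised:

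| Dropouts | Loss | Completers |
|---|---|---|
| 12 | 16.7% | 60 |
| 13 | 18.1% | 59 |
| 14 | 19.4% | 58 |
| 15 | 20.8% | 57 |

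At 13 or 14 dropouts, completers are below 60 while discontinuation is still under 20%, so the two halves of the trigger disagree. The stated purpose of securing 60 completers shows which half governs.

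**5. The subset under the overall rule.** Twelve dropouts leave 60 completers, so replacement is not mandatory. Assume that the 12 fall at random among 72 and that the subset is exactly 42. The subset loss is then hypergeometric with mean 12 × 42/72 = 7, leaving 35 on average.
- P(loss ≥ 8, fewer than 35 remain) = 0.379. Losses of 8 (0.211) or 9 (0.118) make up 0.329 of this, so the shortfall is usually one or two subjects.
- P(loss ≥ 10, 32 or fewer remain) = 0.051.
- P(loss = 12, 30 remain) = 0.0007.

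Sensitivity of P(fewer than 35 remain):
- 12 dropouts, by subset size: 42 gives 0.379, 44 gives 0.076, 46 gives 0.003, 48 gives 0.
- Subset of 42, by number of dropouts: 11 gives 0.239, 10 gives 0.123, 9 gives 0.047, 8 gives 0.010, 7 or fewer gives 0.

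**6. Power for flow stops.** Linear interpolation in Table 11-2, 88.0 + (92.2 − 88.0) × (n − 30)/5:

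| Subset completers | Power |
|---|---|
| 30 (tabulated) | 88.0% |
| 31 | 88.8% |
| 32 | 89.7% |
| 33 | 90.5% |
| 34 | 91.4% |
| 35 (tabulated) | 92.2% |

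A separate Poisson calculation with rates 2 and 1 gives about 90–92% at 33–34 subjects, which agrees. No power figure here uses Table 11-1.

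**The case against.** The strongest reply is that little follows from this. The gap is 3 subjects overall (75 against 72) and 2 in the subset (44 against 42), and every number is given as a minimum. The overall 60 is secured by replacement whatever percentage is written. At a true 20% loss the subset keeps 33 or 34 subjects, and flow-stop power stays above 90%. The 35 is a table entry giving 92.2%, not the point where power crosses 90%, so the 38% overstates the risk; the 5% is nearer the mark. Replacement within the subset is allowed under section 7.4. The rule also looks ahead to likely completers, so it could be invoked before the twelfth loss. Finally, the full analysis set keeps subjects with at least one recorded endpoint, and the mixed model can use a single visit, so a subject who leaves after visit 2 is not a total loss.

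Most of this stands as a limit on size, and is why the point is minor. The last argument means that the probabilities above are upper estimates. It does not make 16.7% into 20%, nor does it supply a completer count for the subset. Permission to replace is weaker than the obligation the plan sets for the secondary endpoint's number.

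A further objection is that 35 should not become a floor while the RV1 inputs conflict: section 11.8 gives standard deviations of 50 and 10 in the text, but 90 and 15 in Table 11-1. That is a separate matter. The 35 is the plan's own stated need, and the floor should be revisited if resolving the conflict raises the RV1 requirement.

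**Conclusion.** The concern holds, as a minor one. The stated 20% discontinuation allowance is wrong as written: 72 and 42 provide 16.7%. The trigger in section 11.8 carries the same error, though its purpose clause limits the harm. The only mandatory replacement rule leaves the subset for both primary endpoints without a completer count.

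The practical effect is small. A subset below 35 has a probability of about 38%, and a subset small enough to take flow-stop power below 90% about 5%. Both assume exactly 12 dropouts spread at random, a subset of exactly 42, no voluntary replacement, and no usable data from subjects who drop out. Modest changes to the first two assumptions reduce the 38% sharply: to 7.6% with a subset of 44, or 1% with 8 dropouts. The extreme case, with all 12 losses in the subset, leaves 30 subjects and 88.0% power, at a chance below 0.1%. These results concern flow stops only and do not show an underpowered trial.

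**What to change.** In section 11.8, keep 72 and 42 and state that they allow for about 16.7% discontinuation. Replace the percentage trigger with completer counts: additional subjects are included when projected completers fall below 60 overall or below 35 in the bladder-emptying subset. Align the permissive wording in sections 7.2.1 and 7.4 with that rule.

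The allowance and the overall trigger are changes of wording only. The subset count may require a few replacements. In the 12-dropout case with a subset of 42, any shortfall is usually 1 or 2 subjects and at most 5 (35 − 30).

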11.9 Level of significance and power

A significance level of alpha 0.05 (2-sided) will be applied.

The power for concluding superiority of the investigational device is at least 90% or higher.

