11.3 Multiplicity control and adjustment of error probabilities

The family-wise Type I error rate will be controlled in a hierarchical fashion in support of demonstrating superiority of the investigational device.

The primary endpoints will be evaluated in a fixed sequence, where the first null-hypothesis must be rejected at a 5% significance level (alpha 0.05) before proceeding with the next.

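### Section 11.9 claims at least 90% power to conclude superiority, but the pass rule needs both primary endpoints and the plan gives only a separate power for each

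*Combined protocol and SAP*

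**What the plan says.** Section 11.9 sets the error rate ("A significance level of alpha 0.05 (2-sided) will be applied") and then gives one power figure for the trial: "The power for concluding superiority of the investigational device is at least 90% or higher".

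Section 11.10 defines success. To show superiority, "the null hypothesis of the primary endpoints must be rejected, at a 5% significance (alpha 0.05"), and the order is "rejecting the null-hypothesis on the first endpoint (Residual urine at first flow-stop) before continuing to the second (Number of flow-stop episodes"). Section 11.3 describes the same gate: "the first null-hypothesis must be rejected at a 5% significance level (alpha 0.05) before proceeding with the next".

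Section 11.8 sizes the two endpoints separately:

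- **RV1.** The last row of Table 11-1 reads "50 (90) 10 (15) 0.05 91.6 % 30": means 50 and 10, SDs 90 and 15, power 91.6%, sample size 30. The caption says "assuming no within subject correlation as a worst-case approach, using proc Power in SAS". The text above the table uses the same 40 mL difference and the same 30 subjects, but SDs of 50 and 10 mL.
- **Flow stops.** Table 11-2 gives 92.2% power at 35 subjects for rates of 2 and 1.
- **Subgroup.** At least 42 of the 72 randomised subjects are measured for both primary endpoints, with 20% discontinuation allowed for.

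The plan reports no power for rejecting both nulls and no assumed correlation between the two endpoints.

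**The concern.** A fixed sequence protects the type I error. It does not make the probability of passing both steps equal to the power of either one. When both must be rejected, the relevant power is the joint one. It can never exceed the smaller marginal power, and it falls below that unless the two tests are very strongly dependent.

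The sponsor and the ethics committees will read section 11.9 as a risk of at most 10% of missing the pass criterion when both planned effects are real. If the 90% belongs to each endpoint separately, that risk is understated. The gap would remain even if Tables 11-1 and 11-2 were both free of error.

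**Working it through.** **1. Inputs.** Two-sided alpha 0.05 (11.9). RV1 difference 40, SDs 90 and 15 in Table 11-1 or 50 and 10 in the text, within-subject correlation 0. Flow-stop rates 2 and 1. Subgroup of at least 42 with 20% loss: 42 x 0.8 = 33.6, so 33-34 completers. (The plan reaches 42 as 35 x 1.2; 35/0.8 would give 44.)

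**2. Reproducing Table 11-2.** Wald test of the log rate ratio: SE = sqrt((1/2 + 1/1)/n). At n = 35, SE = 0.207 and ln 2/SE = 3.35, giving 91.7%. Simulation with a t critical value gives 92.1%, against 92.2% in the plan. This table reproduces.

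**3. Reproducing Table 11-1.**

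- Paired t test, N as total subjects: SD of the difference = sqrt(90² + 15²) = 91.24. At 30, the noncentrality is 40/(91.24/sqrt(30)) = 2.40 and power is 64.1%. The plan says 91.6%.
- Crossover formula with n per sequence: SE = 64.52/sqrt(n), df = 2n - 2. At n = 25, 28 and 30, power is 85.9%, 89.7% and 91.6%, against the plan's 86.0%, 90.0% and 91.6%.

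Of the readings tried (one-sided testing, other within-subject correlations, text SDs, log-scale ratio, two-sample test), only n per sequence matches all three rows. On that reading, 91.6% needs 2 x 30 = 60 subjects.

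**4. Joint power with the table's formula taken at face value.** Entering the subgroup size as n is generous to the plan, since the formula treats n as per sequence. Under independence, joint power is the product; its ceiling is the smaller marginal.

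| n | RV1 | Flow stops | Product | Ceiling |
|---|---|---|---|---|
| 33 | 93.9% | 90.5% | 85.0% | 90.5% |
| 34 | 94.5% | 91.2% | 86.2% | 91.2% |
| 35 | 95.1% | 92.2% | 87.7% | 92.2% |

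The flow-stop power is simulated at 33 and 34, and taken from Table 11-2 at 35.

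If the two test statistics are treated as bivariate normal, joint power at 35 is 89.8% at a correlation of 0.7 and 90.4% at 0.8. At 33 it is 89.9% at 0.95. So 90% needs a correlation of about 0.7 at 35 completers and about 0.95 at 33.

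**5. Table SDs, N as total subjects (the way the text uses 30 and 35).** RV1 power is 64.1% at 30, 69.9% at 34 and 71.2% at 35. Joint power cannot exceed these values whatever the correlation between endpoints. Under independence at 35 it is 0.712 x 0.922 = 65.7%.

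**6. Text SDs, N as total subjects.** SD of the difference = sqrt(50² + 10²) = 50.99. RV1 power is 99.2% at 33 and 99.5% at 35. The products are 0.992 x 0.905 = 89.8% and 0.995 x 0.922 = 91.7%. With the Wald flow-stop power at 33 (SE = sqrt(1.5/33) = 0.213, power 90.2%), the product is 0.992 x 0.902 = 89.5%. The range is about 89-92%.

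**The case against.** The best defence has four parts.

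- **Dependence.** Both endpoints come from the same catheterisation profile, and section 6.3 attributes both to mucosal suction. Positive correlation is therefore plausible and would raise joint power above the product. This stands, but the plan states no correlation, so it cannot be used to confirm 90%.
- **Text SDs.** With 50 and 10 mL, the claim is roughly met at 33-35 completers. This also stands, but it means setting aside the table that section 11.8 cites for the calculation.
- **42 is a minimum.** With 42 completers, the table's formula gives 97.8% x 95.6% = 93.5% under independence. That needs either no loss from the minimum subgroup or recruitment above it, and section 11.9 states neither condition.
- **Hierarchy.** One might argue that a claim on RV1 alone is enough. Section 11.10 speaks of the primary endpoints in the plural and carries the pass criterion through to the second.

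A reader might also infer more than the documents support. Multiplying the tabulated 91.6% and 92.2% gives 84.5%, but this pairs RV1 at 30 subjects with flow stops at 35, and no such trial is planned. The range built on it (83.8% to 91.6%), and the inference that 90% needs near-complete dependence at the planned size, carry the same mismatch. Nor can 64-71% be presented as the trial's established power. It comes from the conflict over SDs and the meaning of N in Table 11-1, which is a separate defect, and it holds on only one reading.

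**Conclusion.** The point holds as a mismatch between the power statement and the pass rule: section 11.9 gives a single figure of at least 90%, and nothing in section 11.8 supports it for rejecting both nulls.

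With the table's own formula and independent endpoints, the shortfall is about 2 to 5 percentage points. The risk of missing the criterion is then about 12% at 35 completers and 15% at 33, rather than 10%.

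The direction is not certain on every reading. The text SDs put joint power close to or just above 90%; the table SDs with N as total subjects put 90% out of reach. The documents do not settle which inputs were intended, so it does not follow that 90% is false under every stated assumption, only that it has not been shown. Type I error control and the analysis models are not affected.

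**What to change.** First reconcile section 11.8: state which RV1 SDs apply (90 and 15, or 50 and 10) and whether N in Table 11-1 is total subjects or subjects per sequence.

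Then restate section 11.9 with:

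- the marginal power of each primary endpoint at one common expected number of subgroup completers;
- the power to meet the section 11.10 criterion (both nulls rejected), under independence and over a stated range of correlation between the test statistics.

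The 84.5% figure should not be inserted, because it mixes two sample sizes.

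The cost is a short calculation and, on most readings, a less favourable stated power. The restatement itself needs no extra patients. If the reconciled figure is judged too low, a larger subgroup is a separate decision, and the wording of at least 42 out of 72 leaves room for it.
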